6.3.3. Safety Population

The Safety analysis population will consist of all subjects with recorded receipt of any amount of study product. The analyses on the Safety analysis population will be performed per treatment actually received.

6.4. Covariates and Subgroups

Subjects will be recruited from multiple clinical sites, and randomization will be stratified by site. No subgroup analyses will be performed. Study day of D5V and treatment indicator will be included as covariates in the linear regression model for clinical improvement at D5V. Similarly, study day of D11V and study day of D28V will be included as covariates in the linear regression model for clinical improvement for D11V and D28V, respectively. Covariates to be included in the multiple imputation models are listed in Section 8.4.

6.5. Missing Data

While all efforts will be made to minimize missing data, some missing data is expected. Whenever possible, subjects terminating from the study early will be given an early termination visit during which the available components of the clinical improvement, DOOR, and their related measures can be recorded. The primary analysis of clinical improvement will use multiple imputation with linear models to impute values using available information (treatment, randomization strata variables, and available visit information), assuming a missing at random (MAR) model. A sensitivity analysis using a tipping point analysis described in Section 8.4.1 will be performed to assess the robustness of the MI model and MAR assumption made about the missing data. Secondary analyses of clinical improvement will further examine the robustness of this analysis using ATP cohorts without imputation. Analysis of DOOR will use the ITT analysis population with missing values of DOOR imputed using multiple imputation. The analysis of DOOR will be repeated using ATP analysis populations with and without imputation of missing data to test the robustness of the multiple imputation model. Details of the multiple imputation models along with pseudocode are provided in Section 8.3.

6.5.1. Clinical Improvement at D5V

Clinical improvement at D5V is defined as fulfillment of all the following 1) Improvement in at least two symptoms present at enrollment (i.e., cough, sputum production, chest pain, or difficulty breathing) or one symptom and at least one vital sign abnormality present at enrollment 2) Absence of deterioration in any qualifying symptom (i.e., cough, sputum production, chest pain, or difficulty breathing); or new vital sign abnormality not present at enrollment 3) Absence of fever in the day preceding or at the D5V 4) No medically attended visit to an ambulatory medical facility (e.g., ED, outpatient clinic, urgent care center) or hospitalization for persistent or worsening LRTI at any time after randomization. Persistent or worsening LRTI is defined as receipt of a non-study antibiotic [parenteral or oral] treatment for LRTI or its complication. However, receipt of a non-study antibiotic after study day 5 will not be regarded as satisfying this definition if it is related to a new non-respiratory process that is unrelated to the prior diagnosis of LRTI.

Subjects will be assessed on whether they were enrolled based on at least two qualifying symptoms (cough, sputum production, chest pain, or difficulty breathing) or based on one qualifying symptom and one abnormal vital sign. Severity recorded on the LRTI Symptoms and Fever form (LRT) for Visit 1 will be used as baseline. Vital signs results recorded on the Vital Signs form (VS1) for Visit 1 and Visit 3 will be used to

derive normal or abnormal results for temperature, pulse, and respiratory rate for baseline and D5V, respectively. Symptoms severity for D5V will be obtained from the Solicited Events form (LRS) for the event date corresponding to the Visit 3 date from the Visit Documentation form (VD4). Normal values for the vital signs are:

- temperature ($<37.8^{\circ}\text{C}$ or 100.0°F),
- pulse (<90 bpm),
- respiratory rate (≤ 20 breaths per minute),

6.5.1.1. Improvement in Two Symptoms or One Symptom and One Vital Sign Present at Enrollment at D5V

For symptoms, clinical improvement at D5V will be defined as presence of at least one-step improvement in two qualifying symptoms present at enrollment. For subjects who qualified based on one symptom and one vital sign, normalization of the presenting abnormal vital sign and at least one-step improvement in the symptom will be considered a clinical improvement.

6.5.1.2. Absence of Deterioration in any Qualifying Symptoms or New Vital Sign Abnormality at D5V

Clinical deterioration at D5V is defined as the deterioration in any qualifying symptoms (i.e., cough, sputum production, chest pain, or difficulty breathing) or presence of a new vital abnormality not present at enrollment. For symptoms, clinical deterioration will be determined as the presence of at-least one step deterioration (worsening from mild to moderate for example) in any qualifying symptom regardless whether the symptom was present at enrollment or not. For vital signs, clinical deterioration will be determined by the presence of new vital sign abnormality that was not present at enrollment.

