## 3.2 Study Outcome Measures

### 3.2.1 Primary Outcome Measures:

The efficacy of azithromycin versus placebo on Day 5 will be based on clinical improvement.

- Clinical improvement will be defined as fulfillment of **all** the following criteria:
  1. Improvement in at least two symptoms present at enrollment (i.e., cough, sputum production, chest pain, or difficulty breathing) or one symptom and at least one vital sign abnormality present at enrollment. For symptoms, at least a one-step improvement (e.g., improvement from moderate to mild cough) will be considered a clinical improvement (Table 1). For vital sign abnormalities, normalization of the

presenting abnormal vital sign will be considered a clinical improvement. Qualifying vital signs and their normal values will include the following:

- temperature (<37.8°C or 100.0°F),
  - pulse (<90 bpm),
  - respiratory rate (≤20 breaths per minute),
2. Absence of deterioration in any qualifying symptom (i.e., cough, sputum production, chest pain, or difficulty breathing); or new vital sign abnormality not present at enrollment. For symptoms, at least a one-step deterioration (e.g. worsening from mild to moderate cough) will be considered clinical deterioration (Table 1).
  3. Absence of fever in the day preceding or at the Day 5 Visit (fever is defined as ≥37.8 °C or 100.0 °F, measured anywhere on the body).
  4. No medically attended visit to an ambulatory medical facility (e.g., ED, outpatient clinic, urgent care center) or hospitalization for persistent or worsening LRTI at any time after randomization (persistent or worsening LRTI is defined as receipt of a non-study antibiotic [parenteral or oral] treatment for LRTI or its complication).  
**Note:** receipt of a non-study antibiotic after study Day 5 will not be regarded as satisfying this definition if it is related to a new non-respiratory process that is unrelated to the prior diagnosis of LRTI

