### 5.1 Subject Inclusion Criteria

Subjects must meet all of the inclusion criteria to be enrolled in this study.

1. Clinician suspected LRTI based on the presence of at least two qualifying symptoms OR one qualifying symptom and at least one qualifying vital sign.

 LRTI will include acute bronchitis, tracheitis, tracheobronchitis, asthma exacerbation, and acute exacerbation of COPD but does not include known pneumonia.

 New cough, worsening of chronic cough, new sputum production, increased volume or purulence of chronic sputum production, chest pain, and difficulty breathing

 Fever (Provider or patient-measured temperature  $\geq 37.8^{\circ}\text{C}$  ( $100.0^{\circ}\text{F}$ ) or patient-reported feverishness), tachycardia of  $\geq 90$  beats/minute, tachypnea of  $>20$  breaths/minute

2. Males and females age  $\geq 18$  years old.
3. Presentation  $\geq 24$  hours and  $\leq 28$  days after the onset of at least one qualifying symptom related to the acute episode of illness.
4. Ability to understand study procedures and willing and able to comply with all required procedures and visits for the entire length of study.
5. Provide written informed consent before initiation of any study procedures.

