For subjects who qualified based on two symptoms, improvement in symptoms at D11V or D28V will be defined as presence of at least one-step improvement in two qualifying symptoms present at enrollment. For subjects who qualified based on one symptom and one vital sign abnormality, clinical improvement at D11V or D28V will be defined as the presence of at least one-step improvement in the one symptom present at baseline. If the one qualifying symptom at baseline has a missing value at D11V or D28V, then improvement in symptoms at D11V or D28V is missing, respectively.

Improvement in fever at D11V or D28V is defined as changing from presence of fever at baseline to absence of fever on D11V or D28V, respectively. Fever will be present at D11V if temperature reported on the LRS form for study day 11 is $\geq 100.0^{\circ}\text{F}$ or if subjective fever is recorded on the LRS form on study day 11. A subject has fever at baseline or at D28V if the subject had subjective fever or a temperature of $\geq 100.0^{\circ}\text{F}$ reported on the LRT form (i.e. LRTTMPF ≥ 100 or LRTFEVYN = Yes) for Visit 1 or Visit 5, respectively. If

at least some of the temperature information is available at D11V or D28V, but none of it indicates objective or subjective fever, then fever is absent at D11V or D28V respectively. If none of the temperature or fever information is available at D11V or D28V, then fever is missing at D11V or D28V, respectively.

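### One-symptom entrants with home or reported fever: read literally, the SAP's Day 5 baseline rule gives them no way to meet the primary endpoint

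*SAP*

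**What the plan says.** **Entry.** Inclusion criterion 1 (Protocol 5.1) accepts two qualifying symptoms "OR one qualifying symptom and at least one qualifying vital sign". Its third footnote defines the fever that qualifies: "Fever (Provider or patient-measured temperature" at or above 37.8°C, "or patient-reported feverishness". No clinic reading is required.

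**Primary endpoint.** Criterion 1 at Day 5 (Protocol 3.2.1, SAP 3.3.2) needs improvement in two enrollment symptoms, or in "one symptom and at least one vital sign abnormality present at enrollment".

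**Derivation.** SAP 6.5.1 first asks whether the subject was enrolled on two symptoms or on one symptom and one abnormal vital sign. It names no form for that step. It then gives the source for vital signs: "Vital signs results recorded on the Vital Signs form (VS1) for Visit 1 and Visit 3 will be used to" set normal or abnormal status for temperature, pulse and respiratory rate at baseline and at D5V. SAP 6.5.1.1 adds that for one-symptom entrants "normalization of the presenting abnormal vital sign and at least one-step improvement in the symptom will be considered a clinical improvement".

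**Fever elsewhere.** SAP 6.5.1.3 counts subjective fever and LRT or LRS temperatures, as well as VS1, when judging fever at D5V. SAP 6.5.2.1 takes baseline fever for the later visits from the Visit 1 LRT form: "A subject has fever at baseline or at D28V if the subject had subjective fever or a temperature of" 100.0°F or more. SAP 8.4.1 uses Day 1 LRT fever in the imputation model, so the field is collected.

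**The concern.** The entry rule and the baseline rule draw on different evidence. Consider a subject with cough alone who felt feverish at home, and whose clinic readings are temperature below 37.8°C, pulse below 90 and respiratory rate 20 or less. This subject is eligible. Under the VS1 rule, nothing beyond the cough can improve.

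The treatment of fever is also lopsided. Subjective fever at Day 5 can make this subject fail criterion 3, yet the subjective fever that qualified the subject for entry cannot count as something that resolved.

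At stake is the primary ITT comparison, which SAP 8.1.1 makes the sole basis for concluding non-inferiority. Subjects who fail by construction in both arms carry no information about treatment and shrink the observed difference. In a non-inferiority trial that is the anti-conservative direction. They also lower the observed improvement rate for a reason unrelated to recovery.

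**Working it through.** The plan gives no figure for this point, so there is none to reproduce. The check has two parts.

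**1. Can the subject succeed?** All Day 5 outcomes were enumerated under the literal SAP 6.5.1 rules: four symptoms graded 0–3, three vital signs normal or abnormal, fever yes/no, and medically attended visit for LRTI yes/no. That gives 4⁴ × 2³ × 2 × 2 = 8,192 states.

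| Baseline | Mild symptom | Moderate | Severe |
|---|---|---|---|
| One symptom, all three VS1 readings normal | 0 | 0 | 0 |
| Same, with entry fever counted as the abnormality | 1 | 2 | 3 |
| One symptom, tachycardia on VS1 | 1 | 2 | 3 |

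Entries are the number of the 8,192 states that meet the endpoint. In the first row none does, including complete recovery. Counting the entry fever makes success possible.

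**2. What would this do to the comparison?** Inputs:
- margin 12.5 points and azithromycin rate 57.6% (Protocol 11.1 and 11.2);
- 674 randomized 1:1, so 337 per arm (Protocol 11.2);
- two-sided 95% interval, so one-sided 2.5%;
- f, the share of randomized subjects affected. The documents do not give it, so it is **assumed** at 2%, 5% and 10%.

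Suppose the true loss on placebo among all other subjects is exactly 12.5 points, and affected subjects fail in both arms.

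- Expected overall loss: d = (1 − f) × 0.125
- Placebo rate: pP = 0.576 − d
- SE = √{[0.576 × 0.424 + pP(1 − pP)] / 337}
- Chance of concluding non-inferiority = Φ[(0.125 − d)/SE − 1.96]

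For f = 5%: d = 0.11875 and pP = 0.45725. SE = √[(0.2442 + 0.2482)/337] = 0.0382. Then 0.00625/0.0382 − 1.96 = −1.796, and Φ = 3.6%.

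| f (assumed) | Expected loss, points | Chance, 337 per arm | Chance, 280 per arm |
|---|---|---|---|
| 0 | 12.5 | 2.5% | 2.5% |
| 2% | 12.25 | 2.9% | 2.9% |
| 5% | 11.875 | 3.6% | 3.5% |
| 10% | 11.25 | 5.1% | 4.8% |

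The 280 column uses the planned ATP-5 size (560 in total). The figures use a normal approximation without continuity correction and ignore the study-day covariate and imputation.

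**The case against.** **The literal reading is not the only one.** SAP 6.5.1 classifies subjects by how they were enrolled, and the presenting abnormal vital sign in 6.5.1.1 could mean the entry fever. A programmer might then treat a normal Visit 3 reading as normalization. Alternatively, the outcome could be treated as undefined, which would exclude the subject from ATP-5 and lead to imputation in the ITT analysis. Under either reading the fixed failures do not arise. This stands. A reader might infer that every subject entering on home or reported fever can never succeed, but the documents do not support that. The problem is confined to observed outcomes, exactly one graded symptom, three normal VS1 readings and the literal rule. A second symptom, or tachycardia or tachypnea on VS1, reopens the route to success. Care-related vital signs are allowed (Protocol Appendix A, note 6), so some provider-measured fevers may reach VS1.

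**The later visits do not show the intended Day 5 rule.** A reader might infer that SAP 6.5.2.1 gets these subjects right because it takes baseline fever from LRT. It does not work that way. Under that section a one-symptom entrant at D11V or D28V needs only the symptom to improve, and the vital sign requirement is absent because vital signs were not recorded at those visits. The LRT definition shows only that the data exist.

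**The size is hypothetical.** Nothing in the documents supports any particular f. The table also sets the margin among subjects able to succeed, whereas the trial's null concerns the defined endpoint in all randomized subjects. A reader might infer a demonstrated breach of the 2.5% level. What is shown is a loss of sensitivity to a real difference, under stated assumptions.

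None of this says which scoring applies, and a primary endpoint should not leave that open.

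**Conclusion.** The point holds in limited form. The SAP's stated source for baseline vital signs is narrower than the entry criterion it has to serve. Read literally, one identifiable group of eligible subjects cannot meet criterion 1 of the primary endpoint in either arm, whatever their recovery. On the other readings the derivation is ambiguous.

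The direction of the effect on the literal reading is clear: toward zero difference, which favours non-inferiority. Its size is unknown. At an assumed 2% it is a quarter of a point; at 10% it is 1.25 points, and the chance of concluding non-inferiority about doubles. These values assume failure in both arms and a true 12.5-point loss in everyone else. The number affected may well be small, but the rule should be settled before treatment codes are seen.

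**What to change.** Amend SAP 6.5.1 and 6.5.1.1 before unblinding:

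- **Scope.** Apply the change only to subjects who qualified on one symptom plus a vital sign and have no abnormality on VS1 at Visit 1.
- **Rule.** For them, take fever on the Visit 1 LRT form (LRTTMPF ≥100.0°F or LRTFEVYN = Yes) as the presenting abnormality. Count it as normalized when criterion 3, absence of fever at D5V, is met.
- **Everyone else.** Leave the baseline definition unchanged. An unrestricted redefinition would let a multi-symptom subject who reported fever succeed on one improved symptom, a wider endpoint change than the problem calls for.
- **Reporting.** Give the number affected by arm, and repeat the primary analysis under the VS1-only rule as a sensitivity analysis.

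The cost is a few lines of SAP text and derivation code, using data already collected. The downside is that for these subjects the vital sign leg rests on reported fever and adds nothing beyond criterion 3. The LRT recall period at Visit 1 is not shown in the documents, so any one-symptom entrant with neither a VS1 abnormality nor LRT fever should be counted separately.

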6.5.1.3. Absence of Fever at D5V

Absence of fever at D5V is defined as absence of fever in the day preceding or at the day of D5V. If the subject had subjective fever or a temperature of $\geq 100.0^{\circ}\text{F}$ reported on the LRT form for Visit 3 (i.e. $\text{LRTTMPF} \geq 100.0^{\circ}\text{F}$ or $\text{LRTFEVYN} = \text{Yes}$), then the subject will be analyzed as having fever at D5V. Similarly, if the subject had subjective fever or a temperature of $\geq 100.0^{\circ}\text{F}$ as reported on the LRS form for the date of the D5V or the day before or if the temperature from the vital sign form (VS1) for Visit 3 is $\geq 100.0^{\circ}\text{F}$, then the subject will also be analyzed as having fever at D5V. If none of the temperature or fever information is available, then absence of fever at D5V is missing. If at least some of that temperature information is available, but none of it indicates objective or subjective fever then the subject has absence of fever at D5V.

6.5.1.4. No Medically Attended Visit or Hospitalization for Persisting or Worsening LRTI at Any Time Post Randomization at D5V

No Medically Attended Visit (MAV) to an ambulatory medical facility (e.g., ED, outpatient clinic, urgent care center) or hospitalization for persistent or worsening LRTI at any time after randomization (persistent or worsening LRTI is defined as receipt of a non-study antibiotic [parenteral or oral] treatment for LRTI or its complication). Note that receipt of a non-study antibiotic after D5V study day will not be regarded as satisfying this definition if it is related to a new non-respiratory process that is unrelated to the prior diagnosis of LRTI. Medically Attended visit information will be recorded on the MAV form.

- If MAVWSCP = ‘Y’ and (MAVABRX = ‘Y’ and (MAVA1RTI = ‘Y’ or MAVA2RTI = ‘Y’ or MAVA3RTI = ‘Y’)), then MAV or Hospitalization for persistent or worsening LRTI at D5V is present.
- If MAVBRX=N or (MAVABRX = ‘Y’ and (MAVA1RTI != ‘Y’ and MAVA2RTI != ‘Y’ and MAVA3RTI != ‘Y’)), then MAV or Hospitalization for persistent or worsening LRTI at D5V is absent.
- If a subject did not complete D5V and had no MAV submitted, then MAV or Hospitalization for persistent or worsening LRTI at D5V is missing.
- Otherwise, if a subject completed D5V but had no MAV submitted then MAV or Hospitalization for persistent or worsening LRTI at D5V is absent.

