### 3.2.2 Secondary Outcome Measures

1. All antibiotic use from Day 1 through Day 11 and from Day 1 through Day 28 in each treatment group
2. The proportion of subjects with one or more unplanned return visits to a physician's office or urgent care for persistent or worsening LRTI from Day 1 through Day 11 and from Day 1 through Day 28 in each treatment group
3. The proportion of subjects with one or more emergency department visits for persistent or worsening from Day 1 through Day 11 and from Day 1 through Day 28 in each treatment group
4. The proportion of subjects with one or more hospitalizations for persistent or worsening LRTI (if not hospitalized at the enrollment visit) from Day 1 through Day 11 and from Day 1 through Day 28 in each treatment group
5. The proportion of subjects exhibiting improvement in at least one presenting symptom at Day 11 and at Day 28 in each treatment group
6. The efficacy of azithromycin versus placebo on Day 11 will be based on clinical improvement. Clinical improvement will be defined as fulfillment of **all** the following criteria:
  - For subjects who qualified based on the presence of at least two symptoms, then improvement must be observed in at least two symptoms present at enrollment (i.e., cough, sputum production, chest pain, difficulty breathing, or fever). For subjects who qualified based on the presence of one symptom and at least one vital sign abnormality, improvement must be observed in the one symptom present at enrollment. For symptoms other than fever, at least a one-step improvement (e.g., improvement from moderate to mild cough) will be considered a clinical improvement (Table 1).
  - **Note:** fever will be objectively ( $\geq 37.8$  °C or 100.0 °F, measured anywhere on the body) or subjectively reported by the subject for the day preceding or on the Day 11 visit. For Day 11, fever will be used similar to what has been done for Day 5 outcome measure definition i.e. clinical improvement requires absence of fever in the day preceding or at the Day 11 Visit.
  - **Note:** vital signs were not recorded at Days 11 and 28. Therefore, the subcomponents of clinical improvement at Day 11 and 28 are different from the subcomponents of clinical improvement used for the primary outcome measure at Day 5 (i.e., subcomponents at Day 11 and 28 do not include any reference to vital signs measures).

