8.1. Primary Efficacy Analysis

The primary efficacy analyses of clinical improvement at D5V will be performed for the ITT analysis population. Clinical Improvement at D5V is defined in Section 3.3.

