- Indicator of subject enrolled at the site with the fourth most number of subjects enrolled (binary indicator)
- Indicator of subject enrolled at the site with the least number of subjects enrolled (binary indicator)
 - Note: the site with the most number of subjects enrolled is reference for site. Language is written to allow for an arbitrary number of sites. In the event of a number of ties for the number of subjects enrolled, tied sites will be ordered in ascending alphanumeric order in the list of model variables.
- Age at enrollment
- Gender (Male is the reference)
- Study day of D5V (centered at 5)
- Presence of fever on Day 1 as recorded on the Assessment of LRTI Symptoms and Fever (LRT) form
- Presence of fever in the day preceding or at the D5V as recorded on Solicited Events or vital signs form

The actual list of MI model variables for each subject-specific imputation model will follow the ordering above but omit variables with missing values. The below pseudo-code / SAS code outlines the creation of 20 multiple imputation datasets. Note that the seeds used in the actual analysis must follow the specification given in the pseudo-code and subjects must be processed in the order described in the pseudo-code. The pseudo-code is for D5V, but the general logic is also applicable to D11V and D28V.

*Outcome variables: clinimprove_D5V

DEFINE i=index variable for subjects having clinical improvement imputed.

Subjects requiring imputation are sorted in ascending order by PATID.

DEFINE N=number of subjects requiring imputation

DEFINE g&i=analysis dataset containing predictors and clinical improvement for

ATP-5 subjects as well as subject i (only one subject not in ATP-5 included). Note that ATP-5 subjects that are missing a value for one or more variables in the subject-specific imputation model are excluded.

DEFINE imp_g&i = g&i, with 20 imputed values for the missing clinical improvement

added by PROC MI

DEFINE &&modelVars_&i = list of observed variables in subject i (treatment group, site1, site2, site3, site4, age, gender, cstday5, fever), to be used for imputation of clinical improvement

Step 1: Imputation model: This model will generate 20 datasets with each dataset containing original complete data along with imputed values for subjects with missing endpoint.

```
%do i=1 %to &N;
```

```
PROC MI data= g&i out= imp_g&i seed= 22131&i NIMPUTE=20 noprint;
```

```
  Var &&modelVars_&i clinimprove_D5V;
```

```

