13. SUMMARY OF CHANGES IN THE CONDUCT OF THE STUDY OR PLANNED ANALYSES

In order to assess the difference in clinical improvement over time, several additional exploratory endpoints were added as described below:

- DOOR analysis based on the number of times clinical improvement was achieved across the three timepoints of D5V, D11V, and D28V.
- DOOR analysis based on the average of daily ordinal outcomes from study Day 1 to Study Day 11
- DOOR analysis based on the average of OCOs from D5V, D11V, and D28V

Additionally, a bivariate analysis of DOOR and number of days of antibiotics use at D5V and D11V will be performed.

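### SAP 6.5.1.3 counts subjective fever alone as Day 5 fever, whereas the primary endpoint definition in protocol 3.2.1 and SAP 3.3.2 requires a measured temperature

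*SAP*

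**What the plan says.** **Definition.** Criterion 3 of the Day 5 outcome in protocol 3.2.1 requires no fever on the day before or at the visit, and states: "fever is defined as ≥37.8 °C or 100.0 °F, measured anywhere on the body". SAP 3.3.2 repeats this. Protocol 11.4.2 item 14, the separate Visit 3 fever analysis, uses the same measured threshold but excludes fever due to a new process unrelated to the LRTI. SAP 8.1 sends the primary analysis to the definition: "Clinical Improvement at D5V is defined in Section 3.3".

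**Derivation.** SAP 6.5.1.3 is the form-level rule. It starts "If the subject had subjective fever or a temperature of" 100.0 °F or more on the LRT form at Visit 3 (LRTTMPF, or LRTFEVYN = Yes). It applies the same either-or test to the LRS form for the visit date and the day before, and adds the Visit 3 vital-sign temperature. Absence is granted only where some information exists and "none of it indicates objective or subjective fever then the subject has absence of fever at D5V".

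**Declared changes.** SAP section 13 says "several additional exploratory endpoints were added as described below", then lists exploratory DOOR analyses and a bivariate analysis. It does not mention the Day 5 endpoint.

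**Passages bearing on intent.** Fever as an entry sign includes a measured temperature "or patient-reported feverishness" (protocol 5.1, note 3). Protocol 3.2.2 item 6 accepts objective or subjective fever at Day 11 and adds: "For Day 11, fever will be used similar to what has been done for Day 5 outcome measure definition".

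**The concern.** The text that will be programmed adds a category that the definition leaves out. Because all four criteria must hold, a subject who meets the other three can have the primary outcome reversed by this one item. The ordinal clinical outcome follows: under SAP 6.5.4 such a subject leaves categories 1 to 4 and, with no medically attended event, falls to 5. The Day 5 DOOR then changes too.

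This is a conflict within the SAP (3.3.2 against 6.5.1.3) as well as between SAP and protocol. No order of precedence is given. SAP 8.1.1 rests the non-inferiority conclusion on this one analysis, so the meaning of success should not be open to argument once results are known.

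**Working it through.** **1. One subject, two rules.** Take a subject who meets criteria 1, 2 and 4, has every reading below 100.0 °F, and reports feverishness on the visit day.
- Protocol 3.2.1 and SAP 3.3.2: no measured fever, so criterion 3 is met and the subject is a success.
- SAP 6.5.1.3: subjective fever is present, so criterion 3 fails and the subject is a failure.

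The reverse cannot arise from the subjective item, which only adds ways to have fever.

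**2. The plan's own figures.** Inputs (protocol 11.2): 57.6% in each arm, margin 12.5 points, two-sided 95% CI with continuity correction, 80% power, 16.9% loss, 560 evaluable, 674 randomised.
- Uncorrected n per arm = 2(0.576)(0.424)(1.96 + 0.8416)² / 0.125² = 245.4, so 246.
- Corrected n = (n/4)[1 + √(1 + 4/(0.125n))]² = 262.
- Power at 280 per arm = Φ[(0.125 − 1/280)/√(2 × 0.576 × 0.424/280) − 1.96] = 82.8%.
- Loss step: 560/(1 − 0.169) = 673.9.

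The loss step reproduces. The 280 per arm is somewhat more than its inputs need, which is conservative and does not affect this point.

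**3. Size per subject.** With 674/2 = 337 per arm, one reclassified subject moves that arm's rate by 100/337 = 0.297 points.

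**4. Effect on the verdict.** The shares reclassified are assumptions. Simulation used 400,000 trials per scenario, 337 per arm, azithromycin rate 57.6% under the definition, Wald 95% CI, and non-inferiority if the lower bound exceeds −12.5 points. It omits missing data, imputation and the study-day covariate, so it simplifies the planned analysis.

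| Share reclassified (azithromycin / placebo) | True difference under definition | Concludes NI, definition | Concludes NI, derivation |
|---|---|---|---|
| 2% / 2% | 0 | 90.7% | 90.2% |
| 5% / 5% | 0 | 90.8% | 89.8% |
| 8% / 8% | 0 | 90.7% | 89.8% |
| 4% / 5% | 0 | 90.8% | 84.4% |
| 3% / 5% | 0 | 90.8% | 77.5% |
| 5% / 4% | 0 | 90.8% | 93.8% |
| 5% / 3% | 0 | 90.8% | 96.4% |
| 5% / 5% | −12.5 | 2.4% | 2.4% |
| 5% / 4% | −12.5 | 2.4% | 4.2% |
| 5% / 3% | −12.5 | 2.4% | 7.3% |

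For scale, 194/337 in each arm gives a lower bound of −1.96 × √(2 × 0.5757 × 0.4243/337) = −7.46 points. Removing 17 placebo successes (177/337) gives a difference of −5.04 and a bound of −12.55. A net placebo excess of 17 subjects would be needed to change that verdict.

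**5. Which rule gave 57.6%?** SAP section 5 reports it as the observed interim rate without naming the fever rule. If it already counts subjective fever as failure, and a fraction f of otherwise improved subjects has subjective fever only, the measured-only rate is 0.576/(1 − f): 58.2% at f = 1%, 64.0% at f = 10%. Power at 280 per arm is then 83.0% to 84.9%.

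**6. Lesser mismatches in the same derivations.**
- *Table 42.* Its footnote takes fever from SAP 6.5.1.3. Protocol 11.4.2 item 14 uses measured fever with the new-process exclusion.
- *Route at Day 5.* Protocol 3.2.1, SAP 3.3.2 and the opening of SAP 6.5.1 let any subject succeed by one symptom plus one vital sign. SAP 6.5.1.1 mentions that route only for subjects who qualified that way. Consider 1 to 4 symptoms, 0 to 3 abnormal signs and every count improved. The eligible profiles number (3+4+5)(1+2+3+4) + 2(2+3+4) = 138. On an exclusive reading, those with at least two symptoms, exactly one improved and at least one sign normalised are discordant: 3 × (1+2+3) = 18. On an inclusive reading none is. These are combinations, not patients.
- *Day 28.* Protocol 3.2.2 item 7 and SAP 3.3.4 require two improved symptoms, fever being countable. SAP 6.5.2.1 accepts one for subjects who entered on one symptom.

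**The case against.** **SAP 6.5.1.3 may state the real intent.** Entry fever includes feverishness, and the Day 11 note accepts subjective fever and likens its use to Day 5. This stands as evidence that intent is open. But the note explains the likeness as requiring absence of fever over the same window. Neither passage amends the Day 5 text, and subjective fever is written out for entry, Day 11 and Day 28 but not for Day 5.

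**The derivation is not left to the analyst.** This stands: SAP 6.5.1.3 fixes one computable rule on named forms and items. The fault is an undeclared departure from the definition, not a missing rule.

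**The harm depends on imbalance.** This also stands. A reader might infer from the lower rows of the table that the trial's type I error is inflated or its estimate biased. The documents do not support that: they give no count and no direction, and the trial is double-blind with matching capsules. Nor are 4.2% and 7.3% error rates under the rule being analysed, where the true differences would be −11.5 and −10.5 points.

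**Two further inferences go too far.** One is that subjects meeting both entry bases are left without any rule at Day 5. SAP 6.5.1.1 can be read so that nothing differs, and the point is one of ambiguity. The other is that the imputation covariate in SAP 8.4.1 ("Presence of fever in the day preceding or at the D5V as recorded on Solicited Events or vital signs form") must match criterion 3. An auxiliary predictor need not, although stating which fever items it uses would help.

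**Conclusion.** The conflict is certain on the text: three passages define Day 5 fever by measurement, and the derivation adds subjective fever without a declared change. It affects the primary endpoint and the Day 5 ordinal outcome and DOOR.

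Its size is unknown. If reclassification is equal in the two arms, at assumed shares of 2% to 8%, power falls by at most about one point and type I error stays near 2.4%. If it is unequal, the estimate shifts point for point with the imbalance, for which the documents offer no basis. The figures assume complete data and treat 57.6% as the measured-fever rate, which the SAP does not confirm.

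This should be fixed, but it does not undermine the design. The route wording and the Day 28 rule are lesser points.

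**What to change.** Before unblinding, reconcile SAP 6.5.1.3 with protocol 3.2.1 and SAP 3.3.2 to one fever rule, in one of two ways:
1. derive criterion 3 from measured temperature, as protocol 3.2.1 and SAP 3.3.2 state; or
2. if subjective fever was intended, amend protocol 3.2.1 and SAP 3.3.2 and declare the change in SAP section 13.

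Report the other rule as a pre-specified sensitivity analysis. SAP 6.5.1.3 already names the measured and subjective items separately, so both can be derived from collected data. State which rule produced the 57.6% interim rate.

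Align Table 42 with protocol 11.4.2 item 14, including its exclusion of fever from a new unrelated process, rather than with criterion 3. SAP 6.5.1.3 names no item for that attribution, so its source needs stating.

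Lesser edits: say in SAP 6.5.1.1 whether a subject with at least two symptoms and an abnormal vital sign may use the symptom-plus-vital-sign route; and bring protocol 3.2.2 item 7, SAP 3.3.4 and SAP 6.5.2.1 to one Day 28 rule.

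The cost is SAP wording, derivation code and one extra analysis. A protocol amendment is needed only if subjective fever is to count or the protocol's Day 28 rule changes.
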